6.4.2 Supplementary Safety Analysis

The primary safety analyses will be repeated for the overall treatment period for the safety analysis set. Here, all events which occurred during the main and extension treatment period will be taken into account. Therefore, a subject will be censored after a primary safety event occurred, or after the date of the EOET visit, or 30 days after study drug discontinuation or after no further data collection happened for a subject (e.g. lost to follow-up).

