#### **9.4.2 Primary Endpoints**

The primary safety analysis is a descriptive time to first primary safety event (for both endpoints: composite of major and clinically-relevant non-major bleeding events [in alignment with ISTH guidelines] and moderate and severe AEs and SAEs).

The primary objective is to assess the safety under an osocimab concentration which is expected to be maintained during a chronic treatment. Thus the aim is to assess the response to treatment while the participant is

- alive (intercurrent event "death") and
- exposed to study intervention (intercurrent event "premature discontinuation of treatment").

Therefore, the time to the first primary safety event is defined as time from first dose of study intervention to the first event of the endpoint of interest up until 30 days after last study intervention in the main treatment period. The time under risk for a participant without a primary safety event will be censored at the date of the EOMT visit, or 30 days after study intervention discontinuation, or at the last date data was collected for a participant (e.g., for participants lost to follow-up) in the main treatment period, whatever occurs first.

The cumulative incidence risk for the primary safety event together with its confidence interval will be estimated. Each of the osocimab groups will be compared to the placebo group using two-sided log-rank tests at a type I error rate of  $\alpha=10\%$ . Due to the explorative nature of these analyses, no multiplicity adjustment will be done.

Hazard ratios comparing each of the osocimab groups with the placebo group and corresponding 90% (and 95%) confidence intervals will be estimated, as appropriate, from Cox proportional hazards models.

Hazard ratio, relative risk reduction (RRR;  $RRR = 100 \times [1 - \text{hazard ratio}]%$ ), and corresponding 2-sided 90% and 95% confidence intervals comparing each of the osocimab groups with the placebo group will be estimated based on two separate Cox proportional hazards models. Censoring will be assumed independent of the randomized group assignment.

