### 9.4.4 Other Analyses

The difference in the median of SQCSs during main treatment period between each of the osocimab groups and the placebo group will be displayed together with the corresponding 90% (and 95%) confidence intervals based on a T-test.

Furthermore, the difference of the proportion of hemodialysis sessions with adequate anticoagulation during main treatment period between each of the osocimab groups and the placebo group will be summarized with the corresponding 90% (and 95%) confidence intervals based on a proportion test.

The difference in the median of AV access bleeding score during main treatment period between each of the osocimab groups and the placebo group will be displayed with the corresponding 90% (and 95%) confidence intervals based on a T-test.

Furthermore, the difference of the proportion of hemodialysis sessions with no AV access bleeding during main treatment period between each of the osocimab groups and the placebo group will be summarized with the corresponding 90% (and 95%) confidence intervals based on a proportion test.

Both the safety and efficacy analyses will be repeated based on the full data to also include events that occurred during the extension treatment period and during the follow-up period.

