4.5 Data Rules

The pre-treatment period serves as baseline period and takes place before first study intervention was given. If there is more than one measurement, the mean of the respective measures will serve as baseline.

Baseline for PD will be visit 5 data prior to dosing.

The primary analysis will be based on all respective events that occurred during the scheduled main treatment period.

Additional analyses may be based on all respective events that occurred during the overall study period, consisting of both the main treatment and extension treatment period.

In addition, further analyses may be based on all events occurring during the full study period consisting of the main treatment, extension treatment and post-treatment follow-up period.

These time scopes are summarized in the table below.

An event is considered treatment emergent if it occurred between start of treatment and not later than 30 days after last administration of study intervention.

An event is considered as full study treatment emergent if it occurred between first study intervention and not later than 5 months after last administration of study intervention.

Additional analysis may be performed post-hoc.

Time scope definition:

Overall study period	Main treatment phase + extension treatment phase
Full study period	Main treatment phase, extension treatment phase + follow up

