6.2.2 Supplementary Analyses

Efficacy Analysis for the overall study period and full study period in SAF

Treatment emergent efficacy events occurring in the overall study period (main and extension treatment period) and the full study period (main, extension and follow-up period) will be analysed similarly as the main efficacy analysis.

Efficacy Analysis in FAS

All efficacy events of the main efficacy variables occurring from randomization until the respective periods (main treatment period, overall treatment period and full study period) will be considered. Similar statistical methods will be applied as for the main efficacy analyses, but the intercurrent event “premature discontinuation of treatment” will be handled following the treatment policy strategy.

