6.4 Safety

6.4.1 Primary safety variables

The composite of major bleeding (MB) and clinically relevant non-major bleeding (CRNMB) events, as assessed by CIAC, and the composite of moderate and severe AEs and SAEs will

be the primary safety endpoints in this study. Only events that started after the first dose of study treatment and during the main treatment period are considered for the primary analysis.

For the primary safety analysis descriptive time to first primary safety event (both treatment emergent AEs and composite of treatment emergent major and CRNMB events [in alignment with ISTH guidelines]) analyses will be performed.

According to the description of the primary estimand, the following events will be considered as competing events for the respective safety endpoint:

- death
- premature end of exposure to assigned treatment (last administration of assigned treatment plus 30 days).

For the primary analysis, the time to event for a subject will be censored at the date of the EOMT visit or after no further data collection happened for a subject (e.g. lost to follow-up).

According to the study protocol (section 7.1.1) one maintenance dose can be missed. If a subject misses a maintenance dose, has a so called administration gap, that lasts longer than 30 days, the subject is not considered at risk for treatment-emergent events during this time until the next dose. When the subject then takes a maintenance dose again, he/she is at risk again. Accordingly there will be additional analyses, where the time not under exposure between two doses will be ignored and events during that time will not be counted. The time under risk will be calculated by removing time between the interrupted dose + 30 days and the next dose and the time more than 30 days after permanent discontinuation to study drug and if occurred the 1st event per patient will be counted. For the primary analysis in this data scope, the time to event for a subject will be censored at the date of the EOMT visit or after no further data collection happened for a subject (e.g. lost to follow-up).

The cumulative incidence function for the event-of-interest as well as the associated competing event(s) together with the corresponding confidence interval will be estimated for each treatment arm using Aalen-Johansen estimators.

The competing event for the primary safety endpoint is death and premature discontinuation of exposure to assigned treatment.

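### SAP 6.4.2 censors at discontinuation plus 30 days in an analysis meant to repeat 6.4.1, where the same point is a competing event; the promised full-study safety repeat also lacks a rule (minor)

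*SAP*

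**What the plan says.** **Main period.** SAP 6.4.1 names two competing events for the primary safety endpoints: death, and "premature end of exposure to assigned treatment (last administration of assigned treatment plus 30 days"). It censors only at the EOMT visit or when data collection ends. Protocol 9.4.2 words this differently: time at risk "will be censored at the date of the EOMT visit, or 30 days after study intervention discontinuation", or at the last date with data.

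**Main plus extension.** SAP 6.4.2 says that the primary safety analyses are repeated for this period in the safety analysis set, and gives the scope as follows: "Here, all events which occurred during the main and extension treatment period will be taken into account". It then says that "a subject will be censored after a primary safety event occurred", or after the EOET visit, "or 30 days after study drug discontinuation or after no further data collection happened for a subject". It does not mention competing events.

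**Full study.** Protocol 9.4.4 covers safety and efficacy alike, and says that both "will be repeated based on the full data to also include events that occurred during the extension treatment period and during the follow-up period". For efficacy, SAP 6.2.2 says that events in "the full study period (main, extension and follow-up period) will be analysed similarly as the main efficacy analysis". SAP 6.4.2 has no counterpart for safety. SAP 4.5 does define a window: an event is "considered as full study treatment emergent if it occurred between first study intervention and not later than 5 months after last administration". SAP 6.4.5 tabulates adverse events over that window.

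**The concern.** One occurrence, the end of exposure after premature discontinuation, has two roles in two adjacent sections, and the second section says that it repeats the first. The role matters for anything on the cumulative-incidence scale. As a competing event, discontinuation leaves the participant in the denominator as someone who can no longer have an on-treatment bleed. As censoring, the participant is assumed to carry the same future bleeding risk as those still on drug. Main-period and overall-period cumulative incidences would then answer different questions under one label. A difference between groups could also appear or vanish according to the rule alone.

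The full-study repeat raises a related question. Under 6.4.1 risk time stops at last dose plus 30 days, and the follow-up visits fall at days 60 to 150 after the last dose. That rule cannot be applied unchanged to an analysis meant to include follow-up bleeds. How discontinuation and death are to be handled there is not written down.

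**Working it through.** The documents give no figure for the effect of the labelling, so there is none to reproduce.

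**Inputs from SAP 9.1 and Protocol 9.2:** placebo bleeding rate λ = 0.10 per year; hazard ratio 1.0; loss to follow-up 0.15 per year (600 × (1 − 0.15 × 0.5) = 555 matches the stated completers); 200 participants per group. Maximum treatment is 18 months, so T = 1.5 years.

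**Assumptions, not in the documents:** discontinuation rate d, death rate m = 0.05 to 0.10 per year, constant hazards, and loss to follow-up independent of bleeding.

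**1. Cumulative incidence under the two rules.** With total competing hazard c,

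CIF(c) = λ/(λ + c) × (1 − exp(−(λ + c)T)).

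The 6.4.1 rule uses c = m + d. The 6.4.2 list, with death still competing, uses c = m.

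| m | d | c = m + d | c = m | gap (points) |
|---|---|---|---|---|
| 0.10 | 0.02 | 12.78% | 12.96% | 0.18 |
| 0.05 | 0.05 | 12.96% | 13.43% | 0.47 |
| 0.10 | 0.10 | 12.08% | 12.96% | 0.88 |
| 0.05 | 0.40 | 10.21% | 13.43% | 3.22 |

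For example, 0.10/0.15 × (1 − exp(−0.225)) = 13.43%, and 0.10/0.55 × (1 − exp(−0.825)) = 10.21%.

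**2. Between-group difference.** Suppose d = 0.30 in one group and 0.10 in the other, with hazard ratio 1.0. The 6.4.1 rule gives 10.91% − 12.51% = −1.60 points (m = 0.05) or 10.55% − 12.08% = −1.53 (m = 0.10). Censoring gives 0. For scale, a simple binomial 90% half-width for the first difference is 1.645 × √(0.1091 × 0.8909/200 + 0.1251 × 0.8749/200) = 5.3 points.

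**3. Hazard-scale results.** A cause-specific Cox model or log-rank test for bleeding removes a participant from the risk set at the same time under either label, so the change is 0.

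**4. Size of the follow-up window.** Day 30 to day 150 after the last dose is 120 days. Taking bleeding and loss to follow-up as the only exits:

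- First bleeds on treatment per group: 200 × 0.10/0.25 × (1 − exp(−0.25T)) = 17.7 at 12 months and 25.0 at 18 months.
- Still event-free and observed: 200 × exp(−0.25T) = 155.8 and 137.5.
- First bleeds in follow-up: that number × 0.10/0.25 × (1 − exp(−0.25 × 120/365.25)) = 4.9 and 4.3, or 28% and 17% on top of the on-treatment count.
- If the rate halves off drug (assumption): that number × 0.05/0.20 × (1 − exp(−0.20 × 120/365.25)) = 2.5 and 2.2, or 14% and 9%.

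No planning rate is given for the second primary endpoint (moderate or severe AEs and SAEs), so its gap is not calculated.

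**The case against.** The strongest reply is that 6.4.2 uses the word censored loosely, as a list of points where risk time ends. Discontinuation plus 30 days is the same date under either label, the section opens by saying that the analyses are repeated, and its wording follows Protocol 9.4.2. This stands in part. It disposes of two stronger readings:

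- A reader might infer that listing the primary event as a censoring reason means no event would be counted. The text places that censoring after the event, so the natural sense is that the event counts and risk time then stops.
- A reader might infer from the silence on death that death is censored too. The word repeated is enough to bring the 6.4.1 treatment of death with it.

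It does not remove the point on discontinuation, because there 6.4.2 states a role, and it is not the one in 6.4.1. Nor does agreement with Protocol 9.4.2 help, since 6.4.1 has already moved away from that wording.

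On the full-study repeat, a reader might infer that follow-up safety goes unanalysed or that the window is open. Neither holds. SAP 4.5 fixes the 5 months, SAP 6 says that follow-up will be considered at study completion, and SAP 6.4.5 provides adverse event tables. Efficacy receives little more than the instruction to proceed similarly. What is open is mainly the handling of discontinuation and death.

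The size could also be overstated. If everyone were treated for only 6 months, follow-up would add 5.6 first bleeds to 9.4 (59%), but the extension is mandatory, so that does not describe a whole group. Protocol 7.1 and SAP 4.2 expect permanent discontinuation in rare instances, which favours the low end of the range in step 1.

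**Conclusion.** SAP 6.4.2 is inconsistent with 6.4.1 on premature end of exposure. Taken as written, it makes the overall-period Aalen-Johansen estimates and differences, the Fine-Gray model and Gray's test depart from the while-on-treatment estimand in SAP 2. The effect on 18-month bleeding incidence is about 0.2 to 0.5 points if discontinuation is rare and about 0.9 to 3.2 points at 10 to 40 per 100 patient-years. Both ranges rest on assumed discontinuation and death rates and constant hazards. Even the unequal-discontinuation example moves the difference by far less than its 90% half-width.

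It would be wrong to infer that the primary safety result or any bleeding hazard ratio is at risk. All analyses are descriptive (Protocol 9.1), and 6.4.2 is supplementary.

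The missing full-study rule is secondary and close to missing detail. It deserves a sentence because SAP 4.4 treats data after the main period as open-label, and SAP 6.5 shows that the primary analysis is already complete. An unwritten choice would therefore be made with results known. Overall severity is minor.

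**What to change.** Amend SAP 6.4.2 before the final analysis.

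1. **Overall period.** State that death and premature end of exposure (last administration plus 30 days) are competing events as in 6.4.1. Censor only at the EOET visit (EOMT for participants who do not enter the extension) or when data collection ends. Remove the primary safety event from the censoring list, which is a wording tidy. Note that this departs from the censoring language of Protocol 9.4.2, as 6.4.1 already does.

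2. **Full study period (supplementary, safety analysis set).** Repeat the time-to-first-event analysis of both primary safety endpoints over the SAP 4.5 window. Death is a competing event, and stopping study drug does not in itself end risk time. State how the end of the 5-month window is treated: as a competing event in line with 6.4.1, or as censoring with the non-informative assumption written out. This needs saying because early discontinuers reach the end of the window sooner. Label the analysis as including off-drug and partly open-label time, as answering a different question from the while-on-treatment analyses, and as specified after the primary analysis.

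The cost is SAP wording and one extra set of tables. The protocol already provides for bleeding to be recorded and adjudicated to the end of follow-up. The drawbacks are few additional events, wide intervals and a rule that postdates the primary results. The primary analysis does not change.

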6.4.3 Other safety analyses

All Bleedings Analysis

The primary safety analyses will be repeated for all bleedings (defined as the composite of MB, CRNMB and minor bleedings) and its components for the safety analysis set.

Bleeding analysis by ISTH category

The descriptive primary safety analysis will be repeated for all major bleedings and their respective ISTH categorization.

BARC Bleedings Analysis

The descriptive primary safety analyses will be repeated for bleeding types 1 to 5, including any sub types, according to the BARC Bleeding Criteria. These are defined as follows:

- Type 0:
 - No bleeding
- Type 1:
 - Bleeding that is not actionable and does not cause the patient to seek unscheduled performance of studies, hospitalization, or treatment by a health-care professional; may include episodes leading to self-discontinuation of medical therapy by the patient without consulting a health-care professional.
- Type 2:
 - Any overt, actionable sign of hemorrhage (e.g., more bleeding than would be expected for a clinical circumstance, including bleeding found by imaging

alone) that does not fit the criteria for type 3, 4, or 5 but does meet at least one of the following criteria:

- requiring nonsurgical, medical intervention by a health-care professional,
 - leading to hospitalization or increased level of care, or
 - prompting evaluation
- Type 3:
 - Type 3a:
 - Overt bleeding plus hemoglobin drop of 3 to < 5 g/dL* (provided hemoglobin drop is related to bleed)
 - Any transfusion with overt bleeding
 - Type 3b:
 - Overt bleeding plus hemoglobin drop ≥ 5 g/dL* (provided hemoglobin drop is related to bleed),
 - Cardiac tamponade,
 - Bleeding requiring surgical intervention for control (excluding dental/nasal/skin/hemorrhoid),
 - Bleeding requiring intravenous vasoactive agents
 - Type 3c:
 - Intracranial hemorrhage (does not include microbleeds or hemorrhagic transformation, does include intraspinal),
 - Subcategories confirmed by autopsy or imaging or lumbar puncture,
 - Intraocular bleed compromising vision.
 - Type 4:
 - CABG-related bleeding,
 - Perioperative intracranial bleeding within 48 h,
 - Reoperation after closure of sternotomy for the purpose of controlling bleeding
 - Transfusion of ≥ 5 U whole blood or packed red blood cells within a 48-h period,
 - Chest tube output more than or equal to 2L within a 24-h period
 - Type 5:
 - Fatal bleeding
 - Type 5a:
 - Probable fatal bleeding; no autopsy or imaging confirmation but clinically suspicious

- Type 5b:
 - Definite fatal bleeding; overt bleeding or autopsy or imaging confirmation

Bleeding Characteristics Summary

The characteristics of all bleedings will be summarized by presenting counts and percentages of events with a certain attribute separated by treatment group.

Pre-Treatment Safety Summary

All safety events that started after randomization and before first dose of study intervention will be summarized by presenting counts and percentages of subjects with efficacy event before start of treatment separated by treatment group.

AV Access Bleeding Score Analysis

Severity of bleeding at the dialysis access will be assessed approx. 15 minutes after removal of the dialysis needle(s) from the AV access according to the following categories (exploratory bleeding score):

- “0” no access bleeding
- “1” slow oozing
- “2” overt bleeding

The mean difference of AV access bleeding score during main treatment period and baseline between each of the osocimab groups and the placebo group by visit will be displayed with the corresponding 90% (and 95%) confidence intervals applying ANOVA with treatment group as factor. The distribution of AV access bleeding score between each of the osocimab groups and the placebo group by visit will be compared using the Wilcoxon Rank sum test. Change in AV access bleeding scores from baseline per visit will be also calculated. Baseline will be the median of all pre-treatment values.

Additionally, a table will be created showing AV access bleeding categories over time per visit, at pre-treatment all values will be shown. Change from baseline per visit will be calculated. This will be done for the full study period. Figures will be provided.

Furthermore, the difference of the proportion of hemodialysis sessions with no AV access bleeding during main treatment period and baseline between each of the osocimab groups and the placebo group will be summarized with the corresponding 90% (and 95%) confidence intervals based on the score method as described by Newcombe (1998).

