6.2.3 Other efficacy analyses

Efficacy Analysis by Component

The main efficacy analysis will be repeated for all single components of the main efficacy variable (MI, stroke (ischemic and undetermined type), major amputation of vascular etiology, acute limb ischemia, symptomatic VTE, systemic embolism).

Analysis of Death Events

The main efficacy analysis will be repeated for all-cause death and for vascular death (Death due to MI, ischemic stroke, pulmonary embolism (PE) and non-CNS systemic embolism (SE)). In addition, frequencies of other reasons (including COVID-19 related) will be displayed by the categories as adjudicated by the CIAC.

Pre-Treatment Efficacy Summary

All efficacy events that started after randomization and before first dose of study intervention will be summarized by presenting counts and percentages of subjects by treatment group.

SQCS Analysis

The effect of osocimab on the clotting in the dialysis circuit will be assessed by the SQCS. Clotting scores will be assigned as follows:

- “0” clean filter and no visible clots in the drip chamber/air trap
- “1” traces of coagulation in the filter and/or in the drip chamber/air trap
- “2” intermediate state between “1” and “3”
- “3” fully clotted extracorporeal system resulting in an interruption of the hemodialysis session

Adequate anticoagulation is defined by a SQCS of less or equal “1”.

The mean difference of SQCS values during main treatment period and baseline between each of the osocimab groups and the placebo group by visit will be displayed together with the corresponding 90% (and 95%) confidence intervals applying ANOVA with treatment group as factor. This will also be repeated for the overall study period. The distribution of SQCS between each of the osocimab groups and the placebo group by visit will be compared using

the Wilcoxon Rank sum test. Change in SQCS scores from baseline per visit will be also calculated. Baseline will be the median of all pre-treatment values.

Percentage of subjects with adequate anticoagulation (SQCS "0" or "1") by visit will be presented.

Additionally, a table will be created showing SQCS categories over time per visit, at pre-treatment all values will be shown. This will be done for the full study period. Figures will be provided.

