6.4.8 Hemodialysis data

Hemodialysis data like heparin dose and Kt/V will be displayed by means of descriptive statistics and change from baseline by visit.

Furthermore, the difference of the proportion of hemodialysis sessions with adequate anticoagulation during main treatment period and baseline between each of the osocimab groups and the placebo group will be summarized with the corresponding 90% (and 95%) confidence intervals based on a proportion test.

Additionally a table will be created showing all heparin values over time per visit, at pre-treatment all values will be shown. Change from baseline per visit will be calculated. Baseline in this case will be the mean of all pre-treatment values. This will be done for the full study period.

Any changes to the dialysis prescription and compliance will be summarized by visit and treatment group.

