7.4 Version 4.0

Version 4.0 of the SAP was finalized on 23 JUN 2022 with the following edits and additions:

Section 4.5.1: It is given that laboratory records without a RAVE Datapage ID (corresponding record in the electronic case report form is missing) will be excluded from the analysis.

8. References

Biostatistics Working Party, EMA/214249/2022; Points to consider on the impact of the war in Ukraine on methodological aspects of ongoing clinical trials; 13 April 2022.

Nelson W. *Applied Life Data Analysis*. New York: Wiley, 1982.

Newcombe RG. Interval estimation for the difference between independent proportions: comparison of eleven methods. *Stat Med*. 1998; 17:873-90.

9. Appendix

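### SAP 6.4.3 puts an independent-proportions interval on repeated dialysis sessions; if main-period sessions are pooled and positively correlated within participants, the interval is too narrow

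*SAP*

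**What the plan says.** SAP 6.4.3 (AV Access Bleeding Score Analysis) plans a between-group comparison of "the difference of the proportion of hemodialysis sessions with no AV access bleeding during main treatment period and baseline", with 90% and 95% intervals by Newcombe's score method. The title given for that method in SAP section 8 (References) begins "Interval estimation for the difference between independent proportions".

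SAP 6.4.8 plans the parallel comparison for clotting in the circuit, "the difference of the proportion of hemodialysis sessions with adequate anticoagulation during main treatment period and baseline", with "confidence intervals based on a proportion test" and no named method. Protocol 9.4.4 uses the same unnamed test for both session proportions and mentions the main period only: "no AV access bleeding during main treatment period between each of the osocimab groups and the placebo group".

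Protocol Table 1–1 schedules both scores at visits 2 to 18 and at EOMT. The AV access score does not apply to catheter users. None of these sections mentions a participant-level summary, a clustered variance or repeated sessions per participant.

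The neighbouring analyses are worded differently. The mean-score comparison in 6.4.3 covers the "AV access bleeding score during main treatment period and baseline between each of the osocimab groups and the placebo group by visit", and SAP 6.2.3 presents "Percentage of subjects with adequate anticoagulation" at each visit.

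**The concern.** The unit counted is the dialysis session, and one participant supplies many. A Newcombe interval takes two event counts and two denominators and treats every session as a separate independent observation. Sessions in the same person, through the same vascular access, are likely to resemble each other. The protocol points that way: sections 8.2.2 and 8.3.7 judge post-dialysis access bleeding against that participant's own recent pattern. With positive correlation, the effective number of observations is smaller than the session count and the interval overstates precision.

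The words about baseline in 6.4.3 and 6.4.8 raise a second problem. They do not say whether baseline is shown separately or subtracted, so two programmers could compute different contrasts. A two-proportion Newcombe interval does not fit a difference of changes.

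In a descriptive study the interval is the main statement of uncertainty, and access bleeding is a safety outcome of an anticoagulant.

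**Working it through.** The plan states no width, coverage or ICC for these analyses, so there is no figure of its own to reproduce.

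**Inputs from the documents**
- Scored sessions per participant (protocol Table 1–1): 18. Visits 2–4 give 3 before treatment; visits 5–18 plus EOMT give 14 + 1 = 15 in the main period.
- About 200 participants per osocimab group and 200 on pooled placebo (protocol 4.1). At most 200 × 15 = 3,000 main-period sessions per group, fewer for AV access because catheter users are not scored.

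**Assumed, not in the documents**
- ICC within participant: 0.05, 0.10, 0.30.
- Proportion of sessions without bleeding: 0.90 for the half-widths.

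**Formulas**
- Design effect: DE = 1 + (m − 1) × ICC, with m sessions per participant.
- Width factor: √DE.
- Approximate coverage of a nominal interval: 2Φ(z/√DE) − 1, with z = 1.645 or 1.960.
- 90% half-width: 1.645 × √(2 × 0.9 × 0.1 × DE / 3000).

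**Main period, m = 15**

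| ICC | DE | Width factor | Effective sessions of 3,000 | 90% coverage | 95% coverage | 90% half-width, points |
|---|---|---|---|---|---|---|
| 0 | 1.0 | 1.00 | 3,000 | 90.0% | 95.0% | 1.27 |
| 0.05 | 1.7 | 1.30 | 1,765 | 79.3% | 86.7% | 1.66 |
| 0.10 | 2.4 | 1.55 | 1,250 | 71.2% | 79.4% | 1.97 |
| 0.30 | 5.2 | 2.28 | 577 | 52.9% | 61.0% | 2.91 |

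Simulation of the Newcombe interval on pooled sessions (beta-binomial participants, 200 per group, no true difference) agrees. With session proportions of 0.50 to 0.95, 90% coverage was about 90% at ICC 0, 79% at 0.05, 70–71% at 0.10 and 53–54% at 0.30. Uneven session numbers (an assumed mix averaging 13.1 per participant) gave similar undercoverage. An interval clustered by participant, on the same session-level difference, covered 89.5% to 90.4% at nominal 90%.

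**Baseline shown separately, m = 3**

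DE is 1.10, 1.20 and 1.60, the width factor 1.05, 1.10 and 1.26, and 90% coverage about 88%, 87% and 81%. When bleeding is very rare the shortfall can vanish: at ICC 0.10 with 99.5% of sessions free of bleeding, simulated 90% coverage was about 93%.

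**Difference in change from baseline**

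Let r be the baseline-to-main correlation divided by the ICC. If the ICC and p(1 − p) are equal in both periods and all 15 + 3 sessions are present, the ratio of true to independent-session variance is

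[(1 + 14 ICC)/15 + (1 + 2 ICC)/3 − 2r ICC] / (1/15 + 1/3) = 1 + ICC × (4 − 5r).

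At ICC 0.10 this is 0.90 for r = 1 (interval too wide) and 1.15 for r = 0.5 (too narrow). The direction of error is therefore not fixed.

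**By visit**

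m = 1, so DE = 1 and Newcombe is valid.

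**The case against.** The SAP does not say that sessions are pooled, so the error depends on an inference. That is fair, but pooling is the natural reading. The sentence counts sessions and omits the visit qualifier that the neighbouring score comparison carries. For SQCS, a by-visit reading of 6.4.8 would largely repeat the percentages already planned in 6.2.3.

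The size rests wholly on assumed ICCs, and nothing in the documents supports a particular value. This stands. The figures show sensitivity and do not predict the trial's result. On the absolute scale, the half-width at 90% bleeding-free sessions moves from 1.3 points to between 1.7 and 2.9.

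A reader might infer that all three sections contain the same demonstrated error. The documents do not support that: SAP 6.4.8 and protocol 9.4.4 do not name their test, so the error there is likely but conditional. What is certain there is the missing specification.

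A reader might also infer that every single-period interval is too narrow whenever sessions are positively correlated. The rare-bleeding baseline case shows otherwise.

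Finally, the scores are tertiary/exploratory (protocol Table 3–1), the analyses are descriptive (protocol 9.1), and by-visit comparisons of the same scores are planned. This limits importance, but it does not make the interval valid.

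**Conclusion.** The concern holds for the main-period comparison in SAP 6.4.3. If sessions are pooled within a group and positively correlated within participants, the stated 90% and 95% intervals are too narrow. Even an assumed ICC of 0.05 roughly doubles the error rate of the nominal 90% interval, from 10% to about 21%. The baseline interval is affected little or not at all. If a difference of changes is meant, the cited method does not fit, and an independent-session interval could err in either direction.

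SAP 6.4.8 and protocol 9.4.4 are exposed to the same problem if their test treats sessions as independent. In both SAP sections the contrast with baseline is undefined.

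It would be tempting to conclude that the trial's bleeding results are unreliable. The documents do not support that: the primary endpoints are time-to-first-event analyses per participant, the by-visit analyses use one value per participant, and no decision rule uses these session intervals. The point is worth correcting but is of limited weight.

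**What to change.** State the contrast once and use it in both 6.4.3 and 6.4.8. For session-level data, replace Newcombe and the unnamed proportion test with an interval clustered by participant: a GEE with identity link, independence working correlation and robust standard errors by participant, or a participant-level bootstrap. Then, according to what was intended:

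- **Differences within one period:** fit treatment group as the only term and show the main-period and pre-treatment differences separately. The point estimates remain the pooled session differences.
- **Difference in change from baseline:** fit group, period and their interaction in the same clustered model, and report the interaction.
- **Results by visit:** say so; Newcombe may then stay.

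If per-participant proportions are preferred, state that the estimand then weights participants equally instead of sessions.

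The cost is small: the data are already collected and the procedure is standard. The main-period intervals will be wider if sessions are positively correlated. SAP 6.5 indicates that the primary analysis was already complete, and SAP 4.4 that it caused unblinding, so a main-period reanalysis should be labelled post hoc.
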